2.4 Treatments (study treatment, rescue medication, concomitant therapies, compliance)

The Safety set will be used for the analyses below. Categorical data will be summarized as frequencies and percentages. For continuous data, mean, standard deviation, median, 25th and 75th percentiles, minimum, and maximum will be presented.

2.4.1 Study treatment / compliance

Duration of exposure, actual cumulative dose, dose intensity (DI) and relative dose intensity (RDI) will be summarized by combination arm, separately for each component of study treatment (PDR001 and appropriate novel agent). The duration of treatment will also be presented for each combination arm. Duration of exposure will be categorized into time intervals; frequency counts and percentages will be presented for the number (%) of subjects in each interval. The number (%) of subjects who have dose reductions or interruptions, and the reasons, will be summarized by combination arm.

Subject level listings of all doses administered on treatment along with dose change reasons will be produced.

The safety set will be used for all summaries and listings of study treatment.

Duration of exposure to study treatment

Duration of exposure to study treatment is considered by taking into account the duration of exposure to PDR001 and any novel agent partner for each combination arm:

Duration of exposure to study treatment (days) for each combination arm = (last date of exposure to study treatment) – (date of first administration of study treatment) + 1.

The last date of exposure to study treatment for each combination arm is the latest of the last dates of exposure to PDR001 or any novel agent partner (see [Table 2-5](#)).

Summary of duration of exposure of study treatment in appropriate time units will include categorical summaries and continuous summaries (i.e. mean, standard deviation etc.) using appropriate units of time.

Duration of exposure to PDR001 and novel agent combination partner

Duration of exposure to PDR001 (days) = (last date of exposure to PDR001) – (date of first administration of PDR001) + 1.

Table 2-5 Definition of last date of exposure of study drug

Scenario	Definition of last date of exposure of study drug	Example
PDR001 LAG525 ACZ885	
The planned end date of the last cycle in which the last non-zero dose of the investigational drug was last administered (i.e last date of administration + (planned interval duration-1day))
 
Note : If the patient died or was lost to follow-up before the derived last date, the last date of exposure to investigational drug is the date of death or the date of last contact, respectively.
	
Example 1: If PDR001, LAG525, or ACZ885 is administered every four weeks, the last date of exposure is the date of administration in the last cycle + 27 days.

	If the derived last date of exposure goes beyond the data cutoff date, it should be truncated to the date of data cutoff.	
INC280	Date of last administration of a non - zero dose of the study drug.	Example 2: A patient had a permanent discontinuation of the study drug 06Jan2013 after being put on a temporary interruption since 01Jan2013. In this case the last date of exposure is- 31Dec2012.
Scenario 1: Novel agent with a cyclic administration other than Q4W	
The planned end date of the last cycle in which the last non-zero dose of the investigational drug was last administered.
 
Note : If the patient died or was lost to follow-up before the derived last date, the last date of exposure to investigational drug is the date of death or the date of last contact, respectively.
 
If the derived last date of exposure goes beyond the data cutoff date, it should be truncated to the date of data cutoff.
	
Example 1: In a once a week administration of an investigational drug, the last date of exposure is the date of administration in the last cycle + 6 days.
 
Example 2: In a 21-day cycle with one or several infusions in the beginning of the cycle, the last date of exposure is the date of first infusion in the last cycle + 20 days.

As more novel agents are combined with PDR001, the above table will be updated, and the novel agents added to the appropriate rows in the above table.

Summary of duration of exposure of PDR001 will include categorical summaries based on 28 day intervals and using descriptive statistics (mean, standard deviation etc).

The duration includes the periods of temporary interruption.

Cumulative dose

Cumulative dose of a study treatment is defined as the total dose given during the study treatment exposure and will be summarized for each of the study treatment components.

The **planned cumulative dose** for a study treatment component refers to the total planned dose as per the protocol up to the last date of investigational drug administration. The planned cumulative dose is not summarized or listed. It is used for relative dose intensity calculations.

The **actual cumulative dose** refers to the total actual dose administered, over the duration for which the subject is on the study treatment as documented in the Dose Administration eCRF.

For patients who did not take any drug the cumulative dose is by definition equal to zero.

For continuous dosing, the actual cumulative dose is the sum of the non-zero doses recorded over the dosing period and the planned cumulative dose is the planned starting dose summed over the same dosing period.

For intermittent dosing, the actual cumulative dose should be defined based on the days when the subject is assumed to have taken a non-zero dose during dosing periods.

Dose intensity and relative dose intensity

Dose intensity (DI) for patients with non-zero duration of exposure is defined as follows:

- **For PDR001, LAG525, and Canakinumab (ACZ885):**
 - $DI \text{ (mg / week)} = \text{Actual Cumulative dose (mg)} / \text{Duration of exposure to study treatment (week)}$.
 - If for example, the duration of exposure to PDR001 is 8 weeks and the patient receives two injections of PDR001 at 400 mg :
 - $DI \text{ (mg/week)} = \text{Actual Cumulative dose (mg)} / \text{Duration of exposure (week)}$
 $= 800 \text{ (mg)} / 8 \text{ (week)} = 100 \text{ (mg/week)}$
- **For Capmatinib (INC280):**
 - $DI \text{ (mg/day)} = \text{Actual Cumulative dose (mg)} / \text{Duration of exposure (in days)}$

For patients who did not take any drug the DI is by definition equal to zero.

Planned dose intensity (PDI) is defined as follows:

- **For PDR001, LAG525, and Canakinumab (ACZ885):**
 - $PDI \text{ (mg/week)} = \text{Planned Cumulative dose (mg)} / \text{Duration of exposure (week)}$.
- **For Capmatinib (INC280):**
 - $PDI \text{ (mg/day)} = \text{Planned Cumulative dose (mg)} / \text{Duration of exposure (in days)}$.

Relative dose intensity (RDI) is defined as follows:

- **For PDR001, LAG525, and Canakinumab (ACZ885):**
 - $RDI = DI \text{ (mg /week)} / PDI \text{ (mg /week)}$.
- **For Capmatinib (INC280):**
 - $RDI = DI \text{ (mg/day)} / PDI \text{ (mg /day)}$.

For each PDR001 and novel agent combination, DI and RDI will be summarized separately for each of the study treatment components, but using the duration of exposure of each of the components.

Dose reductions, interruptions or permanent discontinuations

The number of subjects who have dose reductions, dose escalations, permanent discontinuations, administration stopped/paused during infusion or interruptions, and the reasons, will be summarized separately for each of the study treatment components. Dose reductions and dose escalations are only allowed for Capmatinib (INC280) (see [Table 2-6](#)).

‘Dose changed’, ‘Was drug administration stopped or paused’ and ‘Dose permanently discontinued’ fields from the Dosage Administration CRF pages (DAR) will be used to determine the dose reductions, dose escalations, dose interruptions, administration stopped /paused and permanent discontinuations, respectively.

The corresponding fields 'Reason for dose change/dose interrupted', 'Reason for administration stopped or paused' and 'Reason for permanent discontinuation' will be used to summarize the reasons.

A dose change is either 'change in prescribed dose level' or 'dosing error' where actual dose administered/total daily dose is different from the prescribed dose.

Note: Dose interruptions are captured in the eCRF following the Oncology Data standard Reference manual and CRF Completions Guidelines. Depending on the dosing administration schedule (e.g. continuous dosing, interval dosing), data would be collected in different fashion. For instance, for continuous dosing, an interruption is defined as a dose of zero in a unit of time between two non-zero dosing records. In general, any rest period as part of the regimen/schedule is not considered as an interruption.

For the purpose of summarizing interruptions and reasons, in case multiple entries for interruption are entered on consecutive days/dose administrations with different reasons, separate interruptions will be counted. However, if the reason is the same in this mentioned multiple entries on consecutive days/dose administrations, then it will be counted as one interruption.

Reduction: A dose change where the prescribed dose level is lower than the previous prescribed dose level or where the actual dose administered/total daily dose is lower than the calculated dose amount based on the prescribed dose. Therefore any dose change to correct a dosing error will not be considered a dose reduction. Only dose change is collected in the CRF, number of reductions will be derived programmatically based on the change and the direction of the change.

Table 2-6 DAR record example for capmatinib (INC280)

DAR record number	Prescribed daily dose	Administered daily dose	Dose reduction Yes/No	Comment
1	800	800	No	
2	800	1000	No	Dosing error
3	800	800	No	Correcting dosing error
4	800	600	Yes	Due to AE
5	600	400	Yes	Dosing error
6	600	600	No	Correcting dosing error
7	400	600	Yes	Protocol-prescribed dose reduction (e.g. due to AE), dosing error
8	600	600	No	Dose increase
9	600	400	Yes	Dosing error

10	400	400	Yes	Dose reduction due to lower prescribed dose, although actual dose is not lower than before.
----	-----	-----	-----	---

Note: It is assumed that if dose reduction is yes, that dose change was checked.

Escalation: For capmatinib, if the dose has been reduced per the mandatory dose modification, escalation to the previous dose level is permitted if the following criteria are met.

- A period of 4 weeks of treatment has passed since restarting dosing at the reduced dose level and there is no recurrence of the AE
- Subject is deriving clinical benefit.

Note: A dose rechallenge i.e when a subject goes back to the previous prescribed dose after an interruption, is not considered as an increase.

Missing data: If dose is recorded but regimen is missing or entered as ‘none’, it is assumed that the investigational drug was taken as per-protocol.

Treatment beyond RECIST progression

The number of patients who continue treatment beyond RECIST1.1 progression according to local investigators assessment based on protocol specified criteria will be summarized. It includes all patients who received any study treatment (i.e. at least one dose of any component of the study treatment) after RECIST 1.1 progression assessed by local investigators. Those patients will be identified using the field “Will the subject continue treatment beyond disease progression as per RECIST1.1?” on the Verification for Treatment beyond RECIST1.1 PD CRF pages.

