For drugs administered every 4 weeks (PDR001 and LAG525), the dose intensity and planned dose intensity will be reported in mg/cycle, defined as follows :

- $DI \text{ (mg / cycle)} = (\text{Actual Cumulative dose (mg)} / \text{modified duration of exposure to study treatment (days)}) * 28$, where modified duration of exposure (days) = last date of exposure of study drug (as defined in [Table 2-1](#) above) - (date of first administration of study drug) + 1.

If for example, the duration of exposure to PDR001 is 6 days because patient died 6 days after first day of dosing, the modified duration of exposure to PDR001 used in dose intensity calculation will be 28 days.

- PDI (mg/cycle) is 400 mg/cycle and 600 mg/cycle, for PDR001 and LAG525, respectively.

Dose interruptions or permanent discontinuations

The number of subjects who have dose permanent discontinuations, dose interruptions, and the reasons, will be summarized separately for each study drug, as described in the main SAP for the randomized part of the study.

Treatment beyond RECIST progression

The number of subjects who continue treatment beyond RECIST1.1 progression according to local investigators assessment based on protocol specified criteria will be summarized. It includes all subjects who received any study treatment (i.e. at least one dose of any component of the study treatment) after RECIST 1.1 progression assessed by local investigators. Those subjects will be identified using the field “Will the subject continue treatment beyond disease progression as per RECIST1.1?” on the Verification for Treatment beyond RECIST1.1 PD CRF pages.

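### Main SAP Section 2.4.1: relative dose intensity for the four-weekly antibodies ignores cumulative dose delays under 28 days and so differs from the Arm 1A rule for identical dosing

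*SAP*

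**What the plan says.** Main SAP, Section 2.4.1, for PDR001, LAG525 and canakinumab:

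- DI is actual cumulative dose over duration of exposure in weeks. PDI is planned cumulative dose over duration of exposure in weeks. RDI is DI/PDI.
- Planned cumulative dose "refers to the total planned dose as per the protocol up to the last date of investigational drug administration".
- On which duration to use: "DI and RDI will be summarized separately for each of the study treatment components, but using the duration of exposure of each of the components".
- On gaps in dosing: "The duration includes the periods of temporary interruption".
- For a four-weekly antibody, "the last date of exposure is the date of administration in the last cycle + 27 days" (Table 2-5). This date is cut back at death, loss to follow-up or data cut-off.
- How planned dose accrues is spelled out only for continuous dosing. The matching sentence for intermittent dosing covers actual dose only.

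Arm 1A SAP, Section 2.4.1, for PDR001 and LAG525: "PDI (mg/cycle) is 400 mg/cycle and 600 mg/cycle, for PDR001 and LAG525, respectively". DI is computed over a modified duration that always credits the full last 28-day cycle and is not truncated at death, last contact or cut-off.

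**The concern.** RDI should tell the reader how much of the intended dose per unit time was delivered. In the main SAP a late dose lengthens the duration and so lowers PDI along with DI. PDI then stops being the protocol's intensity and becomes whatever the patient's own timing makes it. Dose reductions are allowed only for capmatinib, so for the antibodies late and omitted doses are a principal reason for RDI to fall, and this formula is blind to delays that total less than one cycle.

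The second problem is consistency. Arm 1A gives PDR001 + LAG525, the combination whose results in randomized Arm 1 led to Arm 1A. One study would report different RDI values for the same dosing history, depending on which SAP applies.

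**Working it through.** **Inputs.** PDR001 400 mg per dose (main SAP worked example); 28-day planned interval and last exposure date = last administration + 27 days (Table 2-5); fixed PDI of 400 mg per 28 days = 100 mg/week (Arm 1A SAP). The main SAP's DI line labels its denominator as exposure to study treatment. I follow the section's closing sentence and its worked example, which use each component's own duration.

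**The plan's own figures.** The example supposes that "the duration of exposure to PDR001 is 8 weeks and the patient receives two injections of PDR001 at 400 mg". DI = 800/8 = 100 mg/week, which reproduces. In the Arm 1A example, one dose followed by death after 6 days' exposure gives a modified duration of 1 + 27 = 28 days, which also reproduces.

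**Algebra.** RDI (main SAP) = (actual/duration)/(planned/duration) = actual/planned. For k full doses with total delay D days, D = (last day − first day) − 28(k − 1):

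- Main SAP, calendar reading (doses the schedule would have given by the last administration date): RDI = k/(k + floor(D/28)).
- Main SAP, one planned dose per cycle started: RDI = k/k = 100%.
- Arm 1A rule: RDI = 28k/(28k + D).

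**Example, Days 1 and 43.** Duration = 43 + 27 = 70 days = 10 weeks. DI = 800/10 = 80 mg/week. Planned by Day 43: Days 1 and 29 = 800 mg, so PDI = 800/10 = 80 mg/week and RDI = 100%. With the fixed PDI, 80/100 = 80%.

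| Dose days | D (days) | Duration (days) | DI (mg/week) | Planned doses, calendar | Main PDI (mg/week) | Main RDI | Arm 1A-rule RDI |
|---|---|---|---|---|---|---|---|
| 1, 29 | 0 | 56 | 100 | 2 | 100 | 100% | 100% |
| 1, 43 | 14 | 70 | 80 | 2 | 80 | 100% | 80% |
| 1, 56 | 27 | 83 | 67.5 | 2 | 67.5 | 100% | 67.5% |
| 1, 29, 71, 99 | 14 | 126 | 88.9 | 4 | 88.9 | 100% | 88.9% |
| 1, 43, 85, 127 | 42 | 154 | 72.7 | 5 | 90.9 | 80% | 72.7% |
| 1, 29, 85 | 28 | 112 | 75 | 4 | 100 | 75% | 75% |

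If planned dose is counted per cycle started, every main-SAP entry is 100%, including the skipped cycle in the last row.

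**Source of the discrepancy.** Dividing by the patient's own duration is harmless if planned dose accrues over that same duration: 400 × (70/28) = 1000 mg, 1000/10 = 100 mg/week, RDI = 80%. The trouble is the mismatch: planned dose stops at the last administration and moves in whole doses, while duration continues to the end of the cycle.

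**Check on a partial fix.** Fixed PDI with the main SAP's truncated duration: one 400 mg dose and 6 days' exposure gives DI = 400/(6/7) = 467 mg/week, RDI = 467%. Doses on Days 1 and 29 with cut-off on Day 36 give DI = 800/(36/7) = 156 mg/week, RDI = 156%. Both read 100% today because duration cancels.

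**The case against.** Delays remain visible elsewhere: DI itself falls to 80 mg/week in the example and is summarized by arm and component, interruptions are tabulated with reasons, and all doses are listed. The tolerability endpoint is interruptions, reductions and discontinuations, not RDI. No Arm 1 versus Arm 1A comparison is planned, and Arm 1A safety tables cover that arm alone. All of this stands. It limits the consequence but does not make the RDI figure right.

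A reader might also infer more than the text supports:

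- That RDI always reads 100% whatever the delay. On the calendar reading it does not: delays totalling 28 days or more and skipped cycles lower it, and at exact multiples of 28 days it equals the Arm 1A value. Only the per-cycle reading, which the SAP does not exclude, gives that result.
- That delays and omissions are the only things that can move RDI for the antibodies. Partial infusions, stopped administrations and dosing errors also change actual dose.
- That a second dose on Day 28 would give 200%. That depends on how the protocol's dosing windows define the planned dose, and the protocol is not at hand.
- That exposure in the two arms cannot be compared at all. Outside truncated patients, DI converts directly (mg/week × 4 = mg/cycle).
- That a trial-wide shift in RDI can be stated. It depends on the frequency and length of delays, which the SAP does not give.

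**Conclusion.** The point holds as a defect in one descriptive derivation. As written, main-SAP RDI for the three antibodies cannot see cumulative delays under 28 days and counts longer ones only in whole cycles. Per patient, the gap from the Arm 1A rule is 20 percentage points for doses on Days 1 and 43 and 32.5 points for Days 1 and 56, shrinking as more doses are given (11.1 points for one 14-day delay in four doses) and vanishing when the total delay is an exact number of cycles. For full doses given on or after schedule, the main SAP never reads lower than the Arm 1A rule, so the error runs in one direction. These figures assume a 28-day interval, full doses, component-specific duration and no truncation. ORR, DoR and the decision rules are untouched. It is worth correcting because the rule gives a wrong result as written and the same study already contains a workable definition.

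**What to change.** In main SAP Section 2.4.1, for PDR001, LAG525 and canakinumab, adopt both parts of the Arm 1A method together:

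1. Define PDI as a fixed value: the protocol dose per administration divided by the planned interval.
2. Compute DI over each component's modified duration, crediting the full last planned interval with no truncation at death, last contact or data cut-off.

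Keep RDI = DI/PDI, and keep the truncated duration for the duration-of-exposure summary itself. Part 1 must not be adopted without part 2, for the reason shown by the 467% and 156% results. The cost is one changed derivation in the SAP and its programming; reported RDI will be somewhat lower for patients with delays.

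### Main SAP dose intensity: the formula's denominator contradicts its own example and closing rule, and cutting exposure at death, last contact or cut-off inflates the result for the four-weekly drugs

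*SAP*

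**What the plan says.** Three places in main SAP Section 2.4.1 bear on the DI denominator for PDR001, LAG525 and canakinumab (ACZ885).

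- **Formula line.** The denominator reads "Duration of exposure to study treatment (week". The same section defines that quantity across both drugs, from the first dose of any component onward: "The last date of exposure to study treatment for each combination arm is the latest of the last dates of exposure to PDR001 or any" partner agent.
- **Worked example under the formula.** It supposes that "the duration of exposure to PDR001 is 8 weeks and the patient receives two injections of PDR001 at 400 mg", and reports 100 mg/week. The duration is that of PDR001 alone.
- **Closing sentence.** DI and RDI are summarized separately by component, "but using the duration of exposure of each of the components".

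The PDI line gives an unqualified duration of exposure. A component duration is defined for PDR001: "Duration of exposure to PDR001 (days) = (last date of exposure to PDR001) – (date of first administration of PDR001) + 1".

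Table 2-5 sets the last exposure date for these drugs at the last dose plus the planned interval less one day, which is + 27 days for four-weekly dosing. It then shortens it. If the patient died or was lost first, "the last date of exposure to investigational drug is the date of death or the date of last contact", and a date beyond the data cut-off is moved back to the cut-off. The main SAP makes no exception for DI.

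The Arm 1A SAP, Section 2.4.1, does make one. It removes these cuts for dose intensity and illustrates this with a patient whose exposure lasted 6 days because of death: "the modified duration of exposure to PDR001 used in dose intensity calculation will be 28 days".

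**The concern.** There are two separate defects.

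The first is a contradiction. A programmer who codes the formula line gets a different DI from one who codes the closing sentence whenever one component stops before the other. The SAP expects that to happen, since it tabulates permanent discontinuation by component.

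The second is a mismatch of numerator and denominator. A four-weekly dose is counted in full on the day it is given, but the time it covers is cut short if the patient dies, is lost or reaches the data cut-off before the cycle ends. The error only goes upward. It is greatest in patients with the least exposure, who can produce extreme values in the reported mean, standard deviation and maximum.

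What is at stake is the accuracy of a descriptive exposure table for the randomized arms.

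**Working it through.** **Inputs from the documents.** 400 mg PDR001 per dose and two doses over 8 weeks (main SAP example); last dose + 27 days, so 28 days per cycle (Table 2-5); 6 days of exposure replaced by 28 (Arm 1A SAP example).

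**1. The plan's own figure.** 2 × 400 mg / 8 weeks = 800/8 = 100 mg/week. This reproduces, and only with PDR001's own duration.

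**2. Formula line taken literally.** The documents give no case in which the partner outlasts PDR001, so the following durations are assumptions.

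| PDR001 doses | Combination exposure (weeks) | DI by formula line (mg/week) | DI by closing sentence (mg/week) |
|---|---|---|---|
| 2 | 12 | 800/12 = 66.7 | 800/8 = 100 |
| 2 | 24 | 800/24 = 33.3 | 800/8 = 100 |
| 2 | 36 | 800/36 = 22.2 | 800/8 = 100 |
| 1 | 24 | 400/24 = 16.7 | 400/4 = 100 |
| 4 | 24 | 1600/24 = 66.7 | 1600/16 = 100 |

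**3. Cut last cycle.** Take k doses given on time every 28 days, with the last cycle cut at day t. The uncut duration is 28k days and the cut duration is 28(k−1) + t days, so DI is multiplied by 28k / (28(k−1) + t).

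For the Arm 1A example case (k = 1, t = 6), the main SAP rule gives 400/(6/7) = 466.7 mg/week. The uncut cycle gives 400/4 = 100 mg/week. The factor is 28/6 = 4.67.

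| Doses k | t = 1 | t = 6 | t = 14 | t = 21 |
|---|---|---|---|---|
| 1 | 28.0 | 4.67 | 2.00 | 1.33 |
| 2 | 1.93 | 1.65 | 1.33 | 1.14 |
| 3 | 1.47 | 1.35 | 1.20 | 1.09 |
| 6 | 1.19 | 1.15 | 1.09 | 1.04 |
| 12 | 1.09 | 1.07 | 1.04 | 1.02 |

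A factor of 2 or more needs a single dose cut by day 14, and 3 or more needs a single dose cut by day 9. If the cut is assumed uniform over the 28 days, the mean factor is 3.93 with one dose, 1.37 with two, 1.21 with three and 1.09 with six.

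**4. RDI.** RDI = DI/PDI. If both use the same duration it cancels, leaving actual over planned cumulative dose. In the 6-day case DI = PDI = 466.7 mg/week, so RDI = 1.00.

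**5. Capmatinib.** Table 2-5 ends its exposure at the last non-zero dose. No planned interval is added, so there is nothing to cut.

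**The case against.** The best reply on the denominator is that Section 2.4.1 largely settles it. The example and the closing sentence agree on the component's own duration, and only the formula label departs from them. That is fair: the sentence quoted above is the sound side of the contradiction. But the formula is the line most likely to be coded, so the label still needs correcting.

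On truncation, the reply is that large values are rare. This also stands. At the primary analysis, expansion-phase patients have at least 9 months of follow-up or have left the study. Nine months is 9 × 30.4375 / 28 = 9.8 cycles. A patient still on uninterrupted dosing then has about 10 doses, and a factor of at most 280/253 = 1.11. The extreme values come from patients cut in their first cycle.

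Three stronger readings are tempting, and the documents do not support them.

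- **RDI of 33% or 100% depending on the sentence followed.** In the 24-week case, 33.3/100 = 0.33 arises only if DI uses the combination duration and PDI the component duration. No sentence directs that mix, and the closing sentence puts both DI and RDI on component durations.
- **RDI distorted by the cut.** It cancels, as step 4 shows.
- **An invalid comparison between Arm 1A and the randomized arms.** None is planned. Arm 1A safety tables contain Arm 1A only, and its DI is reported in mg/cycle rather than mg/week.

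**Conclusion.** Both defects are real and minor. The formula line names a duration that the same section contradicts. Taken literally, it would understate DI to between 0.17 and 0.67 of the component value in the assumed cases. The cut last cycle overstates DI for PDR001, LAG525 and canakinumab: 4.67 times in the case the Arm 1A SAP itself uses, but below 2 times from the second dose and at most 1.19 times with six.

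The factors assume on-time four-weekly dosing. The downward figures also rest on assumed partner durations and on ignoring the example and closing sentence. A reader might infer that DI is routinely wrong by several times in either direction; the calculation does not support that. RDI stands as long as DI and PDI share one duration, and capmatinib is not affected by truncation. The response-rate decision rules and the hypothesis test do not use these summaries.

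**What to change.** In main SAP Section 2.4.1:

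1. In the DI and PDI lines for PDR001, LAG525 and canakinumab, name the denominator as the duration of exposure to the component, so that they agree with the example and the closing sentence.
2. For DI and PDI of the four-weekly drugs, use an uncut last cycle: last dose date + 27 days, with no truncation at death, last contact or data cut-off.
3. Keep the truncated duration of Table 2-5 for the summaries of exposure duration, where it is appropriate.

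Follow the principle of the Arm 1A SAP but do not copy its text. Its DI line still refers to exposure to study treatment before defining the dates by study drug, and its PDI is a fixed 400 or 600 mg/cycle with no duration in it.

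The cost is a few wording changes and one derived variable, for which a derivation already exists in Arm 1A. Data collection, dosing and the efficacy analyses are unaffected.
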